### **Study Intervention**

Usual Care consists as follows:

An attention control where patients are provided handouts from PANCAN and videos from the NPF and study staff contact them monthly over video to administer the surveys for the outcomes but also answer any questions.

After a PDAC diagnosis is made, referrals are made to Medical and Surgical Oncology and Palliative Care, and the patient follows up in the Gastroenterology clinic to discuss the diagnosis and related symptoms. Baseline surveys will be completed at the time of enrollment in both the usual care and CHW-led intervention arms.

The CHW-led intervention arm will receive the same care/referrals as usual care but in addition work with a CHW as follows:

The study visits will take place in person in the clinic, School of Behavioral Health conference room, or the patient's home or virtually using Microsoft Zoom (depending on the patient's preference).

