## **2 PANCREATIC CANCER CHW INTERVENTION**

### **I. PRESURVEY AND INTRODUCE PATIENTS TO DIGITAL APPLICATIONS**

**When?** Within 7 days of diagnosis

**Setting:** in person or by phone. Format: 1 on 1 or in small groups

**Duration:** 1 hr.

**Goal:** Administer surveys before the intervention and introduce patients to the Twillio-SMS and educational videos.

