## 8. **INCLUSION / EXCLUSION CRITERIA**

### **Inclusion criteria:**

- Age 18 to 90
- English or Spanish-Speaking
- Diagnosed with Newly-Diagnosed Pancreatic Adenocarcinoma or has a pancreatic mass on CT/MRI with suspected PDAC and is awaiting biopsy.
- Able to communicate verbally to allow for audio recording to complete an exit-interview
- Must be able to consent

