## **17. DATA COLLECTION AND MANAGEMENT RESPONSIBILITIES**

### **Data Collection**

We will collect baseline demographics data (age, gender, race/ethnicity, date of diagnosis, stage of diagnosis, and treatments) from the patient's chart. We will also administer the following surveys before the first study visit, at 4 weeks and 3 months.

- FACT-HEP (measures HRQoL) - 30 questions
- NCCN-FACT Hepatobiliary-Pancreatic Symptom Index – 18 questions
- Palliative Care Attitude Survey (PCAS-9) – 9 questions
- ACP (Advanced care planning engagement) survey – 4 questions
- Acceptability of intervention measure (AIM) survey – 4 questions
- Technology Comfort (our survey) – 12 questions

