### **Storage**

At the time of patient enrollment each patient will be given a unique identification number. The key that correlates the unique identification number will be stored on a secure encrypted computer at Loma Linda. Apart from the informed consent, all other documents will not have any patient information written on them. They will only have the unique identification number.

RedCap will be used to store all the study data for this study. As described above this data is deidentified and the RedCap ID serves as the unique identification number. After the patient fills out the paper version of the questionnaire the data will be entered in RedCap by a study investigator and then those paper form which do not contain any identifiable information will be shredded.

Then after the data collection is completely entirely for all patients and the study is completed, we will destroy the electronic copy correlating names to keys which was stored on a secure computer at Loma Linda. At this point all the study data will be deidentified and stored in RedCap. When the study analysis is completed then all the data will be deleted from the computer.

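### The protocol's passages on when, how and in what setting the outcome surveys are given conflict; if the arm-specific passages are followed, measurement of the primary outcomes could differ by arm

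*Protocol*

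**What the plan says.** Both primary endpoints are changes in patient questionnaires: the NCCN-FACT symptom index and the FACT-Hep (section 7.c). The protocol says how these are collected in five places.

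- **Section 7.e, Study Intervention, on controls:** "study staff contact them monthly over video to administer the surveys for the outcomes but also answer any questions".
- **Section 7.e, Study Intervention, on baseline:** "Baseline surveys will be completed at the time of enrollment in both the usual care and CHW-led intervention arms".
- **CHW intervention, step I:** the stated goal is "Administer surveys before the intervention and introduce patients to the Twillio-SMS and educational videos". The timing is "Within 7 days of diagnosis" and the setting is "in person or by phone. Format: 1 on 1 or in small groups". The whole contact lasts one hour.
- **Section 17, Data Collection:** "We will also administer the following surveys before the first study visit, at 4 weeks and 3 months". No arm is named.
- **Section 17, Storage:** "After the patient fills out the paper version of the questionnaire the data will be entered in RedCap by a study investigator". Again no arm is named.

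Two further passages bear on baseline timing. The inclusion criteria in section 8 admit a patient who "has a pancreatic mass on CT/MRI with suspected PDAC and is awaiting biopsy". The Randomization text in section 7.e stratifies by disease extent but does not say whether randomisation comes before or after the baseline survey.

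**The concern.** Two of these instructions sit inside procedures that belong to one arm. The monthly video survey is part of the description of the control condition. The presurvey is the first step of a programme that only patients allocated to a CHW would receive. A coordinator who works from those two passages would survey controls by video in a staff contact. The same coordinator would take the CHW arm's baseline in person or by phone, perhaps in a group, in the hour that introduces the intervention's tools. On that route the CHW arm's baseline would also come after allocation.

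Patients will know whether they are working with a CHW, and the primary outcomes are their own reports. If mode, setting or timing follows the arm, its effect on the scores cannot be separated from the effect of treatment afterwards. Baseline timing matters in particular because the endpoint is change and section 18 plans a contrast between baseline and 4 weeks. The background in section 7.a reports, from the team's own cohort of 111 newly diagnosed patients, that 72% had a clinically significant fall in physical and mental well-being at 30 days. Scores therefore move in the very period in which the baseline date is unclear. The pilot also exists to supply a variance for a later trial, and mixed modes and baseline dates could affect that variance as well.

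**Working it through.** The protocol states no figure on this point that could be reproduced, so the check is mainly a comparison of passages.

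| Source | Arm | When | Mode and setting | Who |
|---|---|---|---|---|
| 7.e, control contact | Control | Monthly | Video, within the attention contact | Study staff |
| 7.e, baseline sentence | Both | At enrolment | Not stated | Not stated |
| CHW step I | CHW | Up to 7 days after diagnosis | In person or phone, single or group, with the SMS and video introduction | Not stated |
| 17, Data Collection | Not split | Before first visit, 4 weeks, 3 months | Not stated | Not stated |
| 17, Storage | Not split | Not stated | Paper form | Patient completes, investigator enters |

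**Baseline.** Section 7.e fixes it at enrolment in both arms. Step I fixes it by the date of diagnosis. These need not be the same day, because a patient may be enrolled before biopsy. Section 17 ties it to the first study visit. Section 7.e describes study visits only in connection with the CHW work, so this anchor has no clear meaning for a control.

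**Follow-up.** Section 17 gives two rounds. If the monthly control contacts run for three months (an assumption; the control text gives no duration), they give rounds at months 1, 2 and 3. Months 1 and 3 roughly match 4 weeks and 3 months. Month 2 has no counterpart. No passage gives the mode or the administrator of follow-up surveys in the CHW arm.

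**Mode.** Video, phone and paper all appear. Paper completion fits neither the video nor the phone contact without a further instruction.

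**Scale, for illustration only.** Inputs: 60 patients (section 4), 1:1 allocation (section 7.d), hence 30 per arm with no loss to follow-up. The two-sided 5% level is assumed, and so is the shift *b* in one arm's mean; the documents give neither.

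- Standard error of the difference, in SD units: sqrt(2/30) = 0.258. Half-width of the 95% interval: 1.96 × 0.258 = 0.51.
- Shift in standard errors: 0.1/0.258 = 0.39; 0.3/0.258 = 1.16.
- Chance of a significant result with no treatment effect, 1 − Φ(1.96 − b/0.258) + Φ(−1.96 − b/0.258): 6.7% at b = 0.1, 12.1% at 0.2 and 21.3% at 0.3, against 5.0% with no shift.

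These figures apply to a shift in whatever quantity is compared. A shift in the follow-up score enters in full. A shift in the baseline score enters a raw change score in full and a baseline-adjusted analysis only in part. It does not enter a comparison of follow-up scores alone, which section 18 also plans.

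**The case against.** A reader might infer that the protocol prescribes different measurement by arm: baseline in the CHW session against baseline at enrolment, and monthly surveys against surveys at 4 weeks and 3 months. The documents do not support either contrast. Section 7.e sets baseline at enrolment in both arms, and step I itself places the surveys ahead of the intervention, so it may be a looser account of the same event. The section 17 schedule is not confined to the CHW arm. The disagreement on frequency is therefore between two passages about controls, and it comes down to month 2, which cannot affect the 4-week contrast.

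The other side has three further points.

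- Section 7.e says that the CHW arm receives what usual care receives, with the CHW added. Read literally, the monthly staff contact could belong to both arms.
- Step I does not say that the CHW gives the surveys, and the randomisation text does not say that allocation precedes baseline.
- The recruitment text requires pathology confirmation before the study starts for a patient, which limits how far baseline can precede diagnosis. It does not tie that start to enrolment, however, and any pre-biopsy enrolment would occur in both arms.

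All of this stands against a claim that measurement is confounded with treatment. It does not remove the conflict. The favourable reading requires staff to set aside the arm-specific passages, and nothing in the protocol tells them to. Nor can the matter be left to an analysis plan, since it decides how the data are gathered.

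**Conclusion.** The point holds as an internal inconsistency that should be fixed. The passages in section 7.e, CHW step I and section 17 disagree on the timing, mode and setting of the surveys that supply both primary outcomes. If the arm-specific passages are followed as written, these features could differ by arm and bias the comparison. The documents do not show that this will happen, and they give no size for it. The shift of 0.1 to 0.3 SD is an assumption that serves only to show that a modest measurement difference would not be negligible beside a standard error of 0.258 SD. It is not evidence of bias. Because this is a 60-patient pilot meant chiefly to estimate variance, and because one reading of the text would treat both arms alike, the point falls short of a flaw that invalidates the design.

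**What to change.** State one rule for both arms in section 17, and make section 7.e and the CHW programme refer to it.

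- **Baseline:** complete it after pathology confirmation and before randomisation; at the least, before allocation is disclosed and before any intervention content. Consent can still be taken while biopsy is awaited, so the purpose of early recruitment is kept.
- **Follow-up:** give the outcome surveys at 4 weeks and 3 months, counted from randomisation in both arms.
- **Mode and administrator:** name one mode, and have the same research staff give the surveys in both arms, outside the CHW sessions.
- **Deletions:** take survey administration out of CHW step I and out of the extra monthly control contact. That contact stays as an attention contact.

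The cost is protocol wording and minor re-tasking of the coordinator. No visit is added. If the control contacts run for three months, the control arm has one survey round fewer.

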### **Randomization**

The intervention each patient will receive will be randomized using a uniform random number generator (<https://www.randomize.net/>) with stratification by either metastatic PDAC or resectable/borderline resectable PDAC.

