---

1. **PROTOCOL INFORMATION**

Study Title: To evaluate the preliminary efficacy of our digitally enhanced CHW-led intervention in newly diagnosed PDAC with a pilot randomized controlled trial of 60 PDAC patients comparing the intervention to attention control with usual care

Date: 9/1/2025

Funding Source: DOD/CDRMP

Phase of Study: N/A

Version Date of Protocol: 1.0

3

2. **PRINCIPAL INVESTIGATOR'S INFORMATION**

PI Name, Title: [name], Assistant Professor

Name & Address of Research Institution: Loma Linda University Division of Gastroenterology and Hepatology, [name]

[contact]

Fax #:

Email Address: [[contact]](mailto:[contact])

3. **STUDY PERSONNEL INFORMATION**

Study Staff Name, Title: [name]

[contact]

[contact]

Email Address: [[contact]](mailto:[contact])

Study Staff Name, Title: [name] [name]

[contact]

[contact]

Email Address: [[contact]](mailto:[contact])

4. **STUDY INFORMATION**

Location(s) of Research Activity: Loma Linda University Medical Center

Expected Start/Stop Dates of Research: 07/1/2025 to 07/01/2027

Special Time Sensitivities: Funded through a 2-year grant from the DOD.

Type of Research: Prospective

Anticipated Enrollment number: 60

Patient Population: Patients with pancreatic ductal adenocarcinoma

5. **PURPOSE**

The purpose of this study is to obtain a preliminary estimate of the impact of a community health worker-led intervention by understanding the variance of the primary outcomes (symptom burden and quality of life) using a pilot randomized controlled trial.

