**d. Overall study design**

This will be a pilot randomized controlled trial where we will plan on randomizing patients with PDAC in a 1:1 fashion to receive a digitally-enhanced community health worker intervention that will involve visits with the CHW and digital communication to facilitate care navigation and provide early palliative care engagement or usual care with attention control.

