**e. Study Procedures and Schedule**

**Recruitment of subjects for the study**

To recruit patients for the interviews, we will screen all of the patients who present for endoscopic ultrasound (with biopsy) to the endoscopy unit or pre-procedure clinic at Loma Linda, as well as patients referred to the medical or surgical oncology clinics with a new diagnosis of pancreatic adenocarcinoma. We will recruit patients from our gastroenterology clinic and endoscopic unit and the oncology clinic (the researcher's patients) both in person and over the phone via a telephone call. We will not contact patients outside our clinical practice but will distribute an IRB-approved flyer with our number to oncology clinics that patients can call and leave a voicemail or email us at our secure HIPAA-complaint Loma Linda email address assigned to our study ([[contact]](mailto:[contact])). We will also distribute an IRB-approved letter to other oncologists informing them of the study so they can distribute the flyer to their patients and inform patients who may be candidates for this study. The reason we are including patients with suspected PDAC is to eliminate delays once they receive a diagnosis as patients previously reported a flurry of medical visits in the 2 weeks after diagnosis. However, patients will need to undergo a biopsy and have pathology confirmation before study initiation. Patients found to have other pathology on biopsy than pancreatic adenocarcinoma will be excluded. We will explain the study in person.

or over the phone when they are referred for a pancreatic biopsy or for oncologic care for a new diagnosis of pancreatic cancer. We will explain that we are recruiting them because they have pancreatic cancer and want to study if a community health worker can help patients like themselves navigate care and engage with palliative care better than the current care that patients receive. If they are interested, they will then be consented using written informed consent at their clinic visit in the clinic or prior to their in-person study visit.

When a patient is diagnosed with PDAC, they receive the diagnosis over the phone and follow-up in clinic. They are referred to medical and surgical oncology and to palliative care for supportive care..

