**Exclusion criteria:**

- Biopsy Does not Confirm Adenocarcinoma of the Pancreas

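### The two randomisation strata give no place to eligible patients whose disease is non-metastatic but neither resectable nor borderline resectable

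*Protocol*

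**What the plan says.** Section 7.e (Randomization) names one stratification factor with two levels. Patients are randomised "with stratification by either metastatic PDAC or resectable/borderline resectable PDAC". No third level is given, and no rule for a patient who fits neither.

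Eligibility is wider. The disease criterion in section 8 reads "Diagnosed with Newly-Diagnosed Pancreatic Adenocarcinoma or has a pancreatic mass on CT/MRI with suspected PDAC and is awaiting biopsy", with no limit on stage or resectability. The single exclusion is "Biopsy Does not Confirm Adenocarcinoma of the Pancreas". Section 4 describes the population in the same unrestricted way ("Patient Population: Patients with pancreatic ductal adenocarcinoma"), and section 7.d speaks of "randomizing patients with PDAC in a 1:1 fashion". The recruitment text in section 7.e draws on the endoscopy unit, the pre-procedure clinic and the medical and surgical oncology clinics without filtering by stage.

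The planned size is 60 (section 4: "Anticipated Enrollment number: 60"). Section 17 takes "date of diagnosis, stage of diagnosis, and treatments" from the chart at baseline but does not list the stage categories. For the comparison between groups, section 18 names a t-test and a Wilcoxon rank-sum test. It also plans generalized linear models for the change from baseline to 4 weeks. No stratum term is mentioned in either place.

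**The concern.** A stratification factor has to give every eligible patient exactly one level at the moment of randomisation. Here the wording presents two alternatives as if they were the whole set, but the eligibility criteria admit a third kind of patient. When such a patient arrives, someone has to choose a stratum without a written rule, and two members of staff, or one on two occasions, may choose differently.

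Disease extent is worth balancing in this trial. The background (section 7.a) puts 5-year survival at 12% overall and 44% in local-stage disease, and reports impaired and worsening quality of life in patients on palliative chemotherapy. The primary outcomes are symptom burden and quality of life. With 60 patients, chance imbalance on a prognostic factor is a practical worry, and stratification is the protection the protocol has chosen.

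This is not a detail that a statistical analysis plan could supply later. The protocol itself states the levels, and they are used when each patient is randomised, so an analysis document cannot repair the assignment afterwards.

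**Working it through.** The protocol gives no figure to reproduce on this point. The check is whether the two levels together cover the eligible population.

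**Step 1: cross metastatic status with resectability.**

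| Group | Eligible under section 8? | Stratum in section 7.e? |
|---|---|---|
| (a) Metastatic | Yes | Yes, first level |
| (b) Non-metastatic, resectable or borderline resectable | Yes | Yes, second level |
| (c) Non-metastatic, neither resectable nor borderline resectable | Yes | None named |

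**Step 2: look for text that closes the gap.** Three things would do so: a third level, a rule for unclassified patients, or an eligibility limit that removes group (c). None appears. Sections 4, 7.d, 7.e (recruitment) and 8 all describe the population without reference to stage, and section 8 excludes only on biopsy result.

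**Step 3: size.** The number affected is 60 × p, where p is the share of group (c) among those enrolled. The protocol gives no value for p. These values are assumptions chosen only to show the scale:

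- p = 0.10: 60 × 0.10 = 6 patients
- p = 0.20: 60 × 0.20 = 12 patients
- p = 0.30: 60 × 0.30 = 18 patients

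These count patients without a named stratum, not patients misallocated or lost. The gap in the rule exists whatever p is; one such patient exposes it.

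**Step 4: effect on allocation and analysis.** If a group (c) patient is put into either stratum before the allocation is drawn, the arm is still assigned at random and 1:1, so no bias follows. If every such patient goes to the same stratum, the factor is still well defined and little is lost. The loss comes from inconsistent placement: the levels then no longer mean one thing, and balancing within them balances disease extent less well.

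**Step 5: timing.** The pre-intervention survey is due within 7 days of diagnosis (intervention outline, part I), while section 7.a cites a study with a two-week delay from diagnosis to the oncology clinic. The protocol does not say when staging is settled relative to randomisation. It is an inference, but resectability may still be open for some patients when a stratum is needed, which is a further reason to fix the source of the classification in writing.

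**The case against.** The strongest reply is that the either/or wording shows a simple metastatic versus non-metastatic split was meant, and that the second level is only loosely labelled. That may well be the intention, and it would make the cure a single clause. But the text names only resectable and borderline resectable disease, so the written rule does not say it.

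A second reply is that little depends on this in a pilot. Section 5 seeks a preliminary estimate and the variance of the primary outcomes, and an incomplete stage label prevents neither. This stands, and it limits the severity.

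Several stronger readings are tempting but not supported:

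- **That the allocation or the two-arm comparison is biased.** It is not, because assignment within whichever stratum is chosen remains random.
- **That eligible patients will be turned away, changing the population or slowing accrual.** Eligibility is set by section 8, and nothing permits exclusion for want of a stratum.
- **That a stratum-adjusted analysis will be corrupted.** Section 18 describes none.
- **That 6 to 18 patients is an estimate.** It is 60 multiplied by an assumed share.
- **That the change is certain to come before the first patient.** Section 1 dates the protocol 9/1/2025, whereas section 4 gives an expected start of 07/1/2025, so enrolment may already have begun.

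**Conclusion.** The point holds as a should-fix correction. The strata in section 7.e do not cover the population admitted by section 8: patients with non-metastatic disease that is neither resectable nor borderline resectable are eligible but have no stratum. That is a contradiction between two stated rules and does not depend on any assumption.

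The consequence is limited to weaker balance on disease extent, and only so far as placement is inconsistent. It also assumes that allocation within strata is restricted in some way, such as blocking, which the protocol does not describe; without that, stratification gives little balance to lose. The number of patients concerned cannot be derived from the protocol. The validity of the comparison between arms is not threatened.

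**What to change.** 1. **Make the levels exhaustive.** One option is metastatic versus non-metastatic, the latter taking in all other disease. A third level, or a sentence saying which existing stratum group (c) enters, would equally close the gap. With 60 patients, two levels keep the strata larger than three would.
2. **State the source.** Assign the level from staging recorded before randomisation, so that it cannot depend on who enrols the patient.
3. **Use the factor in the analysis.** Include it as a covariate in the between-arm comparison, for example in a linear model with arm and stratum. The between-group tests named in section 18 are unadjusted: they remain valid after stratified allocation, but they forgo the precision that a prognostic stratification factor can give. If a statistical analysis plan already provides for this, nothing further is needed.
4. **If randomisation has started,** document how any group (c) patients were classified, and record the date from which the revised levels apply.

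Before the first randomisation the cost is a sentence or two in the protocol and a relabelled level in the randomisation system. Stage is already to be collected under section 17, so no extra patients or procedures are needed. After enrolment has begun, the change also requires an amendment to a running system and the record described in item 4.
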